#### **6.4.5.5 Assessment of Causality**

The investigator's assessment of an AE's relationship to IMP will be part of the documentation process, but it is not a factor in determining what is or is not reported in the

study. If there is any doubt as to whether a clinical observation is an AE, the event should be reported.

The relationship or association of the test article in causing or contributing to the AE will be characterized using the following classification and criteria:

- Unrelated: This relationship suggests that there is no association between the IMP and the reported event.
- Possible: This relationship suggests that treatment with the IMP caused or contributed to the AE, ie, the event follows a reasonable temporal sequence from the time of IMP administration or follows a known response pattern to the IMP, but could also have been produced by other factors.
- Probable: This relationship suggests that a reasonable temporal sequence of the event with IMP administration exists and, based upon the known pharmacological action of the drug, known or previously reported adverse reactions to the drug or class of drugs, or judgment based on the investigator's clinical experience, the association of the event with the IMP seems likely. The event disappears or decreases on cessation or reduction of the dose of IMP.
- Definite: This relationship suggests that a definite causal relationship exists between IMP administration and the AE, and other conditions (concurrent illness, progression/expression of disease state, or concurrent medication reaction) do not appear to explain the event. The event reappears or worsens if the IMP is re-administered.

#### **6.4.5.6 Exceptions**

While the following events may fulfill the serious criteria, they do not need to be reported as SAEs: hospitalizations/emergency room stays lasting less than 24 hours not meeting other serious criteria, hospitalizations for baseline conditions that do not worsen after starting study participation, hospitalizations for elective procedures anticipated or scheduled prior to study participation, and events expected as part of progression of disease under study.

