#### **6.4.5.2 Eliciting and Documenting Adverse Events**

All AEs (serious and nonserious) will be assessed beginning at screening and up to 42 days after the last dose of IMP.

Serious AEs that occur more than 42 days after the last dose of IMP need not be reported unless the investigator considers them related to IMP.

At every study visit, subjects will be asked a standard nonleading question to elicit any medically related changes in their well-being. They will also be asked if they have been hospitalized, had any accidents, used any new medications, or changed concomitant medication regimens (both prescription and over-the-counter medications).

In addition to subject observations, AEs identified from any study data (eg, laboratory values, physical examination findings, ECG changes) or identified from review of other documents that are relevant to subject safety will be documented on the AE page in the eCRF.

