#### **6.4.5.3 Reporting Adverse Events**

All AEs reported or observed during the study will be recorded on the AE page in the eCRF. Information to be collected includes drug treatment, dose, event term, time of onset, investigator-specified assessment of severity and relationship to IMP, time of resolution of the event, seriousness, any required treatment or evaluations, and outcome. Adverse events resulting from concurrent illnesses, reactions to concurrent illnesses, reactions to concurrent medications, or progression of disease states must also be reported. All AEs will be followed to adequate resolution. The Medical Dictionary for Regulatory Activities (MedDRA, Version 17.1) will be used to code all AEs.

Any medical condition that is present at the time that the subject is screened but does not deteriorate should not be reported as an AE. However, if the subject's condition deteriorates at any time during the study, it should be recorded as an AE.

Any AE that meets SAE criteria ([Section 6.4.5.1](#)) must be reported to the sponsor (designee) immediately (ie, within 24 hours) after the time study center personnel first learn about the event.

Study center personnel should complete the AE eCRF using electronic data capture, designating the event as serious. If electronic data capture is unavailable, complete an SAE form using the following contact information:

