## 10 Study Management

### 10.1 Monitoring

#### 10.1.1 Independent Data Safety Monitoring Board

A DSMB will be established that includes a panel of at least 3 independent members to include medical experts and an unblinded biostatistician. An official charter will be established and approved by all members and Galectin Therapeutics Inc. The primary role of the DSMB will be to periodically monitor the safety of the clinical study. The DSMB will meet at several predetermined times during the study and at any other time when it is determined by the DSMB or Galectin Therapeutics Inc that such a review is warranted. An organizational meeting will be held prior to the first subject randomly assigned to IMP to review and approve the DSMB Charter and to review the output to be provided to the DSMB for scheduled reviews. In addition, an unblinded monitoring team will be established.

The first scheduled DSMB review meeting will be after the first 30 subjects in the study have received 7 doses of IMP. The purpose of this early look at safety is to ensure that there are no unexpected AEs in the population being evaluated in this study. The second scheduled DSMB review meeting will occur after approximately 50% of the total number of subjects to be enrolled has received 13 doses of IMP. The DSMB will then meet again after 50% of subjects have received 26 doses of IMP.

At the first DSMB meeting, the panel will also evaluate GR-MD-02  $C_{\max}$  plasma levels after Infusion Visits 1, 2, 3, and 4 for the first 30 subjects. There should be approximately 10 subjects who received 2 mg/kg and 10 subjects who received 8 mg/kg in this group of subjects. With the aid of a clinical pharmacologist on the panel, the DSMB will assess  $C_{\max}$  levels as a surrogate for systemic exposure, with increasing number of doses in the groups receiving IMP and compare the levels to the safety margins indicated by long-term animal toxicology studies.

The investigative study center staff, subjects, the sponsor and its representatives, and representatives of the CRO, except those responsible for providing unblinded data to the DSMB, will remain blinded throughout the full duration of the study until after the database is locked at the conclusion of the blinded treatment period.

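### The SAE exception for expected disease progression names no events and sets no limit for fatal or drug-related ones, so SAE reporting and SAE tables can be incomplete and vary by site

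*Protocol*

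**What the plan says.** Protocol Section 6.4.5.3 sets the general rule. AEs that result from concurrent illness "or progression of disease states must also be reported" on the AE page, and any AE that meets the SAE criteria "must be reported to the sponsor (designee) immediately", meaning within 24 hours. The site makes that report by completing the AE form and designating the event as serious.

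Section 6.4.5.6 then lists exceptions: "While the following events may fulfill the serious criteria, they do not need to be reported as SAEs". The last item on the list is "events expected as part of progression of disease under study". No events are named and no other section is cited.

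Two nearby sections deal with causality. Section 6.4.5.5 says of the relationship assessment that "it is not a factor in determining what is or is not reported in the" study. Section 6.4.5.2 says that SAEs more than 42 days after the last dose "need not be reported unless the investigator considers them related to IMP".

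On oversight, Section 10.1.1 states: "The primary role of the DSMB will be to periodically monitor the safety of the clinical study". The output for its scheduled reviews is left to the charter and an organizational meeting.

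**The concern.** In compensated cirrhosis, a variceal bleed, an episode of encephalopathy or a liver-related death may be the natural course of the disease or may be harm from the drug. A single case seldom tells which. Comparison between randomized arms does, provided that every site captures and classifies the events in the same way. The exception works against this. Whether a serious liver event counts as an SAE depends on whether the site regards it as expected, and the protocol gives no standard for that judgment. At stake are prompt notice to the sponsor and the completeness of the by-arm serious-event tables.

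**Working it through.** No arithmetic applies to the rule itself, since it rests on no rate, effect size or sample size. The check is to set the sections side by side.

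1. **Is there a list of exempt events?** Not in Section 6.4.5.6. The only list of progression events is the efficacy composite (Protocol Sections 2.2 and 7.2; SAP Sections 2.2, 3.2.2 and 8.2), and the exception does not point to it. That list has ten components. Two are scores (Child-Turcotte-Pugh rise, MELD) and two are endoscopic findings (new varices, larger varices), which leaves 10 − 2 − 2 = 6 clinical ones: hemorrhage, ascites, bacterial peritonitis, encephalopathy, transplant listing or transplant, and liver-related mortality. The last of these is fatal by definition.

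2. **Does the exception stop at death?** No. The first item in the same list, stays under 24 hours, applies only if no other serious criterion is met. The progression item carries no such limit. Death is serious under Section 6.4.5.1, and the opening words of the exception cover events that are serious.

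3. **Does relatedness bring an event back?** Not in the text. Section 6.4.5.2 has an explicit relatedness condition for late SAEs. Section 6.4.5.6 has none, and Section 6.4.5.5 keeps causality out of the reporting decision.

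4. **What record remains?** The waiver covers reporting as an SAE, not recording as an AE, so under Section 6.4.5.3 the event still goes on the AE page. Whether it keeps a serious flag is not settled. Seriousness is among the items collected for each AE, but designating the event as serious is also how a site reports an SAE. A site that uses the exception may therefore leave the flag off.

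5. **Which SAP tables depend on the flag?** Of the categories in SAP Section 9.1, five do: SAEs; serious TEAEs; serious and grade 3 or greater TEAEs; serious TEAEs leading to discontinuation; and serious TEAEs leading to death. No rule adds exempted events back. An exempted liver death could thus be counted among TEAEs leading to death and be missing from serious TEAEs leading to death. The all-TEAE, grade 3 or greater, discontinuation and fatal-AE tables do not need the flag.

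6. **What does the DSMB see?** Section 10.1.1 and SAP Section 12 set three scheduled safety reviews but do not say that serious progression events or cirrhosis complications are shown by arm. The charter is not among the documents.

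7. **Is there a related carve-out?** Yes. Section 6.4.7 keeps clinically significant laboratory findings associated with the underlying disease out of both AE and SAE reporting, unless they are more severe than expected for the subject.

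**The case against.** The strongest reply is that little is lost. Progression events are still recorded as AEs. Cirrhosis complications are assessed at 13 infusion visits (Table 12-2), every four weeks from Week 5 to Week 49 and again at Week 51. AEs are monitored at every infusion visit. The SAP has TEAE, grade 3 or greater and fatal-AE tables, transaminase-with-bilirubin and albumin criteria (Section 9.2), and complications by treatment group (Section 8.2). A reader might infer from the exception that serious liver harm would be hidden from the DSMB, or would go unseen until the final efficacy table. The documents do not support either inference. These other routes exist, SAP Section 12 has the DSMB review safety data and not SAEs alone, and the charter may already call for complications by arm.

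A second reply is that a general rule followed by a section of exceptions is ordinary drafting and not a contradiction. That is fair, although neither section refers to the other.

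A third reply is that the clause is narrower than it looks. Subjects with prior decompensation are excluded, Section 6.2.5 expects nearly 100% one-year survival, and an event attributed to the drug is not, on an ordinary reading, expected disease progression. A careful investigator could read it that way. Another could read it the other way, most easily for events rated possibly related, and the text does not choose between them.

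These replies limit the consequence but do not remove it. None of the other routes gives 24-hour notice or fills the serious-event tables. The grade 3 or greater table is also a weaker support than it seems, because Section 6.4.5.4 asks investigators for mild, moderate or severe while SAP Section 9.1 tabulates grades 1 to 5.

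**Conclusion.** The point holds in a limited form. Following Section 6.4.5.6 as written, a site may leave a serious liver event, including a fatal or possibly drug-related one, out of 24-hour SAE reporting. If the serious flag goes with it, the event is also lost from the SAP's five serious-event categories. The loss can differ between sites. The event should still be found in the other AE tables. For the DSMB, the documents support only this: the protocol does not ensure that these events reach it as serious or by arm.

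The size cannot be computed, because the documents give neither a rate of serious hepatic events nor an expected number of exempted ones. The conclusion rests on two assumptions: that at least some of the clinical complications will meet the serious criteria, and that at least some sites will use the exception.

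**What to change.** - **Section 6.4.5.6:** limit the progression exception to expedited (24-hour) reporting. Name the clinical complications from Section 7.2 that it covers, without the score-based and endoscopic-only components. Apply it only to events that meet the serious criteria, are non-fatal and are judged unrelated to study drug.
- **eCRF and SAP Section 9.1:** flag every such event as serious and count it in the SAE and serious-TEAE tables, whichever way it was notified.
- **DSMB:** tabulate serious progression events and cirrhosis complications by arm at each scheduled review, if the charter does not already provide for this.
- **Reconcile:** refer to the exception in Section 6.4.5.3. State in Section 6.4.5.5 that causality may affect the speed of notification but not whether an event is recorded. Align Section 6.4.7 so that its laboratory carve-out and the revised exception use the same terms.

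The cost is protocol and SAP wording, some extra SAE data entry and one table. Design, sample size and efficacy analysis are unaffected.

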#### **6.4.5.7 Follow-Up of Subjects Reporting Adverse Events**

All AEs must be reported in detail on the appropriate page in the eCRF and followed to satisfactory resolution, until the investigator deems the event to be chronic or not clinically significant, or until the subject is considered to be stable.

### **6.4.6 Pregnancy**

Pregnancy is not regarded as an AE unless there is a suspicion that an IMP may have interfered with the effectiveness of a contraceptive medication. Any pregnancy that occurs during study participation must be reported using a clinical study pregnancy form. The pregnancy must be followed up to determine outcome (including spontaneous miscarriage, elective termination, normal birth, or congenital abnormality) and status of mother and child, even if the subject was discontinued from the study. Pregnancy complications and elective terminations for medical reasons must be reported as an AE or SAE. Spontaneous miscarriages must be reported as an SAE.

Pregnancy must be reported in the same manner as an SAE to PPD Pharmacovigilance by the study center within 24 hours of being informed of the event. If a pregnancy occurs during the study, study treatment must be discontinued immediately (or per sponsor directive), and the pregnancy report form submitted to PPD Pharmacovigilance via the SAE fax line. The study center should submit the pregnancy follow-up form to document the outcome of the pregnancy (health of the neonate). In the event of a miscarriage, therapeutic abortion, death in utero, or the pregnancy outcome leads to an SAE for the mother, follow the Procedure for Reporting an SAE ([Section 6.4.5.3](#)). In the event of a congenital anomaly, an SAE form for the baby must be completed.

Any SAE occurring in association with a pregnancy that is brought to the investigator's attention after the subject has completed the study and considered by the investigator as possibly related to the study treatment must be promptly reported to Galectin Therapeutics Inc.

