2. Cirrhosis or advanced bridging fibrosis wherein the subject has greater than 5 years of obesity (body mass index [BMI] >30) and/or diabetes with negative viral hepatitis markers and a biopsy showing cirrhosis or advanced bridging fibrosis with any amount of fat

Subjects who meet all of the inclusion criteria and none of the exclusion criteria will proceed to randomization and the treatment phase. Subjects who fail to meet eligibility criteria due to an abnormal laboratory result may undergo retesting of the abnormal laboratory parameter during the screening window and at the discretion of the investigator and with prior approval of the medical monitor.

**Treatment Phase:** Subjects with portal hypertension who meet all of the other criteria for study inclusion will be randomly assigned (1:1:1) to receive 1 of 3 treatment assignments including placebo, GR-MD-02 in a dose of 2 mg/kg lean body mass, or GR-MD-02 in a dose of 8 mg/kg lean body mass administered every other week over a 52-week period for a total of 26 infusions. During the treatment phase of the study, all subjects randomly assigned to IMP will attend study visits according to the schedule of visits for study administration and monitoring (Table 12-2). Safety (12-lead electrocardiogram [ECG], physical examinations, vital sign measurements, adverse event [AE] monitoring, and safety laboratory assessments), and efficacy (FibroScan, MBT (if available), biomarkers, assessment of cirrhosis complications [esophageal variceal hemorrhage or portal hypertensive gastropathy

hemorrhage, clinically apparent ascites, spontaneous bacterial peritonitis, overt hepatic encephalopathy, listing for a liver transplant or the performance of a liver transplant], and quality of life) will be monitored throughout the treatment phase.

**Postdose Final Visit (14-28 days):** All subjects will attend a visit (or visits) 14 to 28 days after final dose. During this visit, safety (AE monitoring and safety laboratory assessments) and efficacy (FibroScan, MBT [if available], biomarkers, EGD, HVPG, and a liver biopsy) assessments will be collected/performed ([Table 12-2](#)).

**Follow-up/Early Termination Visit:** All subjects are to attend a follow-up/early termination visit 14 days after the postdose final visit to evaluate safety. During this visit, a 12-lead ECG, a physical examination, vital sign measurements, and AE monitoring will be collected/performed ([Table 12-2](#)).

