#### **4.1.1 Inclusion Criteria**

Each subject must meet all of the following criteria to be enrolled in this study:

1. Has a HVPG measurement  $\geq 6$  mm Hg.
2. Has a liver biopsy with advanced bridging fibrosis (Ishak stage 4) or cirrhosis (Ishak stage 5 or 6), presumably due to NASH. A liver biopsy diagnosis of advanced bridging fibrosis or cirrhosis, presumably due to NASH will include the following 2 categories:
  - a. Advanced bridging fibrosis or cirrhosis with a definitive pathological diagnosis of NASH (presence of fat, ballooning degeneration, and inflammation) or;
  - b. Advanced bridging fibrosis or cirrhosis wherein the subject has greater than 5 years of obesity (BMI  $>30$ ) and/or diabetes with negative viral hepatitis markers (hepatitis B and hepatitis C) and a biopsy showing any amount of fat.
3. Is  $\geq 18$  years of age and  $\leq 75$  years of age at the time of screening.
4. Is willing and able to provide written informed consent prior to the initiation of any study-specific procedures.
5. Is not pregnant and must have a negative serum pregnancy test result prior to randomization.

6. If a fertile man or woman participating in heterosexual relations, agrees to use effective means of contraception (ie, 2 effective methods of contraception, one of which must be a physical barrier method).
  - Effective forms of contraception include condom, hormonal methods (birth control pills, injections or implants), diaphragm, cervical cap, or intrauterine device throughout his/her participation in this study and for 90 days after discontinuation of study treatment. Surgically sterile males and females are not required to use contraception provided they have been considered surgically sterile for at least 6 months. Surgical sterility includes history of vasectomy, hysterectomy, bilateral salpingo-oophorectomy, or bilateral tubal ligation. Postmenopausal women who have been amenorrheic for at least 2 years at the time of screening will be considered sterile.
7. If a lactating woman, agrees to discontinue nursing before the start of study treatment and refrain from nursing until 90 days after the last dose of study treatment.
8. If a man, agrees to refrain from sperm donation throughout the study period and for a period of 90 days following the last dose of IMP. Female subjects may not begin a cycle of ova donation or harvest throughout the study period and for a period of 90 days following the last dose of IMP.

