## **4.2 Withdrawal of Subjects from the Study**

The duration of the study is defined for each subject as the date a signed written informed consent is provided through the last follow-up visit, up to 42 days following the last IMP infusion.

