### **6.1.3.12 Infusion Visit 26 (Week 51 ± 3 Days)**

The following procedures and assessments will be performed prior to administration of IMP:

- Enter the IWRS and register subject visit data.
- CLDQ (This questionnaire will be given to the subject at the beginning of the visit and will be considered source documentation.)
- Assessment of cirrhosis complications.

- Perform a limited physical examination (including weight and examination of the heart, lung, and abdomen).
- Collect vital sign measurements (including heart and respiratory rate, blood pressure, and body temperature).
- Perform hematology testing.
- Perform blood chemistry testing.
- Obtain MELD score.
- Collect plasma and serum sample for freezing at  $-20^{\circ}\text{C}$ .

The following information will be collected after IMP administration:

- Obtain Child-Turcotte-Pugh score and class (A, B, or C).
- AE monitoring.
- Record concomitant medications.

The following will be collected 2 hours after the end of the IMP infusion:

- Collect PK sample

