### **6.1.5 Follow-up/Early Termination (Week 57 ± 3 Days)**

Fourteen days after the previous visit ([Section 6.1.4](#)), the following information will be collected ([Table 12-2](#)):

- Enter the IWRS and register subject visit data
- Perform a 12-lead ECG assessment
- Perform a limited physical examination (including weight and examination of the heart, lung, and abdomen)
- Collect vital sign measurements (including heart and respiratory rate, blood pressure, and body temperature)
- AE monitoring

- Record concomitant medications

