**Table 12-2 Schedule of Events - Randomization, Treatment Phase, and Follow-up/Early Termination**

Infusion Visit	0	1	2, 3, 4, 5, 6	7	8, 9, 10, 11, 12	13	14, 15, 16, 17, 18, 19	20	21	22, 23, 24, 25	26	14-28 Days After Final Dose	14 Days After Previous Visit/ET
Week ± 3 days		1	3, 5, 7, 9, 11	13	15, 17, 19, 21, 23	25	27, 29, 31, 33, 35, 37	39	41	43, 45, 47, 49	51	53-55	57
IWRS	R	X	X	X	X	X	X	X	X	X	X	X	X
FibroScan	A	X a				X						X	
MBT (if available)	N					X						X	
CLDQ b	D	X									X		
Alcohol TLFB b	O	X	X - Inf Visit 5		X - Inf Visit 9	X	X - Inf Visit 17		X	X - Inf Visit 25			
Limited physical examination c	M	X	X	X	X	X	X	X	X	X	X	X	X
Urine pregnancy test d	I		X - Inf Visits 3, 5	X	X - Inf Visits 9, 11	X	X - Inf Visits 15, 17, 19		X	X - Inf Visits 23, 25			
Vital sign measurements e	Z	X	X	X	X	X	X	X	X	X	X	X	X
Hematology f	A	X		X		X		X			X	X	
Blood chemistry g	T	X		X		X		X			X	X	
MELD score	I					X					X		
Biomarkers blood sample h	O	X				X						X	
Plasma and serum sample for storage	N	X				X					X		
IMP administration i		X	X	X	X	X	X	X	X	X	X		
12-lead ECG						X							X
Child-Turcotte-Pugh score						X					X		
EGD j												X	
HVPG j												X	

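### Mandatory pregnancy reporting ends with study participation, 28 to 42 days after the last dose, although contraception is required for 90 days

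*Protocol*

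**What the plan says.** Four parts of the protocol bear on this.

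- **Scope of the report.** Section 6.4.6: "Any pregnancy that occurs during study participation must be reported using a clinical study pregnancy form". Such a pregnancy is then followed to outcome, even if the subject has been discontinued.
- **End of participation.** Section 4.2 defines the duration of the study for each subject as running from consent "through the last follow-up visit, up to 42 days following the last IMP infusion". Section 3.1 places the final visit relative to the one before it: "All subjects are to attend a follow-up/early termination visit 14 days after the postdose final visit to evaluate safety". Table 12-2 labels that column "14 Days After Previous Visit/ET" and puts it at Week 57. The last infusion is at Week 51 (Section 6.1.3.12).
- **Contraception.** Inclusion criterion 6 applies "throughout his/her participation in this study and for 90 days after discontinuation of study treatment". The synopsis also gives 90 days after the last dose.
- **After the last visit.** The closing paragraph of Section 6.4.6 requires a report of a pregnancy-associated serious adverse event that the investigator considers possibly related to treatment. Section 6.4.5.2 requires serious events after day 42 to be reported only if considered related. Neither route has an end date. The post-study telephone contacts (Section 6.1.6, Table 12-3) cover survival, transplant and liver complications; pregnancy is not listed.

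**The concern.** The sponsor chose 90 days as the period in which conception should be avoided, so that is the period in which it would want to know about a conception. The reporting rule stops earlier. After the last visit, a pregnancy outcome is recorded only if it is serious, reaches the investigator and is thought at least possibly related to the drug. Uneventful pregnancies and events judged unrelated leave no record, so an adverse outcome that is reported has no denominator to be set against. Pregnancy outcomes not collected prospectively are hard to recover later.

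What is at stake is the completeness of a small part of the safety follow-up. No efficacy endpoint, error rate or power calculation depends on it.

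**Working it through.** **Inputs**

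- Last infusion: Week 51 (Section 6.1.3.12, Table 12-2).
- Final visit: Week 57 (Section 6.1.5, Table 12-2).
- Postdose visits: the first 14 to 28 days after the last dose, the second 14 days later (synopsis, Study Design; Section 3.1).
- Stated maximum from last infusion to end of study: 42 days (Section 4.2).
- Contraception period: 90 days (criterion 6; synopsis).
- Drug measurable through 72 hours after a dose, then undetectable (Section 2.5).

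**Step 1. Reproduce the plan's 42 days.** From the week numbers: (57 − 51) × 7 = 42. From the visit spacing: 28 + 14 = 42. From the synopsis postdosing period of up to 6 weeks: 6 × 7 = 42. All three agree with Section 4.2.

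**Step 2. Earliest end of participation.** If the first postdose visit is on day 14 and the second is timed only as 14 days later, the last visit is on day 14 + 14 = 28.

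**Step 3. Gap = 90 − day of last visit.**

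| Last visit | Gap | Share of the 90 days |
|---|---|---|
| Day 42 (nominal) | 90 − 42 = 48 days | 48/90 = 53% |
| Day 28 (earliest) | 90 − 28 = 62 days | 62/90 = 69% |

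A ±3-day window on the final visit would give 90 − 45 = 45 to 90 − 25 = 65 days, but a last visit on day 45 would exceed the 42-day limit in Section 4.2. The range used here is therefore 48 to 62 days.

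**Step 4. What falls in the gap.** Only pregnancies that *begin* after the last visit. One that began during participation and is recognised later is still in scope and is followed to outcome.

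**Step 5. Exposure in the gap.** The last measurable level is at 72 hours, that is, day 3. With a last visit on day 42 the gap opens on day 43, which is 43 − 3 = 40 days later. With a last visit on day 28 it opens on day 29, which is 29 − 3 = 26 days later. The percentages in Step 3 are shares of calendar time, not of exposure or risk.

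**Step 6. Number of subjects.** SAP Section 4.2 assigns about 52 + 52 = 104 of 156 subjects to active drug. The documents do not say how many could conceive, so no expected number of pregnancies can be given.

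**The case against.** The case against has several parts.

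- **The scope limit is partly inferred.** Section 6.4.6 does not define study participation; Section 4.2 defines the duration of the study. Section 6.4.6 also says pregnancy is to be reported within 24 hours of the site being informed, with no end date. This stands as a caution: the narrow scope is a reading. It is the better reading, because the 24-hour sentence governs manner and timing, and criterion 6 itself treats participation and the 90 days as two separate periods.
- **The outcomes that could signal harm keep a route.** This stands. A congenital anomaly is serious by definition (Section 6.4.5.1), and the threshold in Section 6.4.6 is only a possible relationship. A reader might infer that nothing after the last visit is ever reported; the text does not support that.
- **Exposure is negligible by then.** Largely stands, within the assay's 1.2 µg/mL limit of detection. A reader might infer 48 days of unmonitored fetal exposure; Section 2.5 does not support that. It does not explain why the reporting period is shorter than the sponsor's own precautionary period.
- **The extension study may cover many subjects.** Possible. Its protocol is not among the documents, and subjects who do not enter it remain uncovered.
- **Other text may exist.** The protocol supplied is the original of 20 February 2015. The SAP describes features it lacks, such as nondosing pharmacokinetic visits, so later protocol text probably existed. Consent pages were also removed. Neither can be checked.
- **Nothing in the documents says the two periods must match.** True. The argument is that they sensibly should, not that a stated rule is broken.

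A reader might also infer that pregnancies in partners of male subjects are excluded. Criterion 6 does bind men ("If a fertile man or woman participating in heterosexual relations, agrees to use effective means of contraception"), but Section 6.4.6 is silent on partners. That is a separate question and adds nothing to the 48 days.

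**Conclusion.** The mismatch is real on the text supplied. Pregnancies beginning after the last follow-up visit but within the 90-day contraception period have no required report unless an associated serious event is considered possibly related (Section 6.4.6) or related (Section 6.4.5.2). The gap is 48 days nominally and up to 62.

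The conclusion rests on reading study participation in Section 6.4.6 as the period defined in Section 4.2, and on no later protocol text or extension-study rule closing the gap.

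It is a minor safety follow-up gap. Drug was undetectable after 72 hours, the number of subjects able to conceive is unknown but probably small, and efficacy is unaffected. It merits correction because the correction is nearly free.

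**What to change.** In Section 6.4.6, require reporting and follow-up to outcome for any pregnancy that occurs during study participation or within 90 days after the last dose, whichever ends later. Keep participation as the starting point: beginning the window at the first infusion would narrow the present rule, since Section 4.2 starts each subject's study at consent.

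In Table 12-3 and Section 6.1.6, add one pregnancy question to the Month 6 telephone contact for subjects who do not enter the extension study. By then the 90 days have passed, so a single question covers the whole period. It would also help to find a late on-study conception, because the last scheduled urine test is at Infusion Visit 25 (Week 49).

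With reporting extended to day 90 the gap is 90 − 90 = 0 days. The cost is one sentence, one question in a call already scheduled, and a small added reporting burden.

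Optionally, and separately, state whether partner pregnancies are reportable over the same period; if so, partner consent would be needed.
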